6 STATISTICAL CONSIDERATION

6.1 Primary Endpoint

Primary outcome= Percent of eligible patient participants who enrolled in the study. The investigators will assess enrollment rate into the study. The investigators aim to have at least 50% of screened patients consent and enrollment. This is a pilot study and as such, our sample size was selected based largely on feasibility. Specifically, we examined the expected margin of error for varying recruitment and recruitment yields.

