key criteria for Inclusion and Exclusion:	
Receive care in the UNC Cardiology or General Internal Medicine practice
 
Have a clinical diagnosis of HF
 
Currently prescribe a loop diuretic
 
Have a New York Heart Association class II-IV
 
Must speak English
 
Must have a working telephone or live with the patient

	
Family Member Eligibility
 
Must be at least 18 years old and able to give informed consent
 
Must be willing to participate in the intervention activities and provide informed consent
 
Must speak English
 
Must have a working telephone or live with the patient

	
Health Care Provider Eligibility
 
Must be an MD or advance practice provider (NP or PA) in the UNC cardiology or General Internal Medicine practice
 
Must be willing to have an enrolled patient visit audio-taped

Number Of Subjects	Up to 80 participants, including up to 30 HF patients and family members, and HCPs
Study Duration	
Each subject’s participation will last up to 6 months
 
The entire study is expected to last 1 year

Study Phases Screening Study Treatment Follow-Up	
(1) Screening: screening for eligibility and obtaining consent and (2) Intervention: study intervention; and (3) 2-day post clinic visit and 1 month follow-up

Efficacy Evaluations	
Primary outcome: Percent of eligible patients and companions who enrolled in the study.
 
Secondary outcomes: 1) mean acceptability checklist score, 2) mean score on self-care of heart failure index scores (maintenance, management, and confidence subscales); 3) mean score on caregiver contribution to self-care of heart failure index scores (maintenance, management, and confidence subscales); 4) mean score on perceived efficacy in patient-physician interactions score; 5) mean score on communication with physicians measure

Pharmacokinetic Evaluations	N/A
Safety Evaluations	N/A
Statistical And Analytic Plan	This is a pilot study and as such, our sample size was selected based largely on feasibility. Specifically, we examined the expected margin of error for varying recruitment and recruitment yields.
DATA AND SAFETY MONITORING PLAN	We will not have a DSMC, DsMC, or DMC for this study given that the safety risk to participants is extremely low.

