3.4 Study Population. We will enroll HF patients, family members, and HCPs

Patient Eligibility

Ambulatory adult patients \geq 30 years old
Receive care in the UNC Cardiology or General Internal Medicine practice
Have a clinical diagnosis of HF
Currently prescribe a loop diuretic
Have a New York Heart Association class II-IV
Must speak English
Must have a working telephone or live with the patient

Family Member/Companion Eligibility

Must be at least 18 years old and able to give informed consent
Must be willing to participate in the intervention activities and provide informed consent
Must speak English
Must have a working telephone or live with the patient

Health Care Provider Eligibility

Must be an MD or advance practice provider (NP or PA) in the UNC cardiology or General Internal Medicine practice
Must be willing to have an enrolled patient visit audio-taped

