After initial identification, we will query HCPs of potentially eligible patients to confirm the diagnosis of HF. (based on their clinical assessment), determine if the patients are appropriate to approach for possible study participation (procedures we have successfully used in our prior studies). When we provide participating providers with a list of their potentially eligible patients, we will all ask them to check how often the patient has a companion enter the exam room with them (none of the time, rarely, some visits, most visits, every visit). Patients will be considered "likely to be accompanied" if the provider indicates that a companion enters the exam room "most visits or every visit." We anticipate that the providers will be very accurate in predicting patients who usually bring a family member into the exam room, since these will be their regular patients. This method will be used to facilitate more efficient recruitment of patients most likely to be eligible for the study. For patients deemed ineligible by providers, we will ask providers to provide reasons why the patients should not be contacted, Provider approved patients will be approached by a research assistant (RA) to assess eligibility and possible interest in the study either during a scheduled clinic visit, via a provider-approved letter, or via telephone using an IRB approved telephone script. For those presenting for a clinic visit, the RA/SC will approach them about participation in the study. If they are interested, the study staff will consent the patient at that time and administer the baseline survey. If there isn't time to complete the entire baseline survey before the visit, we will finish the remainder of the survey either after the visit or via phone within the week of the visit.

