We will use several approaches to identify and enroll family members: 1) If a family member has accompanied the patient to the clinic visit, the family member will be approached by a study coordinator at that time about participation in the study and they can provide written consent at that time, if they are interested and eligible. They will also be administered the baseline survey either before (or after the visit depending on the time) or via phone in the week of the visit. 2) If a family member is not present with the patient at a clinic visit, an IRB-approved study recruitment letter and a copy of the consent form will be sent home with the patient to give to a family member who may be interested in participating, and the family member can contact a study coordinator to discuss the study and/or mail in the signed consent form. The study team will provide a pre-paid self-addressed envelope to return the signed consent form. After receiving signed consent form, the study team will call the potential participants to schedule the baseline study interview for both members of the dyad. For potential participants identified through the CDW or from the HF social support and family studies registry, the study team will mail an IRB approved recruitment letter to potential patient participants. The letter will notify the patient that a family member (preferably who one attends medical visits with them) is required to also participate in the intervention, so they should discuss the study with family members and get their permission to share their contact (phone number or address) with the study team. The letter will include an opt-out form that potential participants may return using pre-paid, self-addressed envelope that will accompany the recruitment letter. We will follow-up with potential patient participants via telephone 1 week after the letters have been mailed. If they are interested in participating and have identified a family member who is interested, the study team will obtain verbal consent from each person and a written consent form will also be mailed to them to sign and return to the study team. The RA/Project Coordinator will also schedule the baseline study interview. If the patient and family member provide verbal consent, but do not return the written consent form via mail, we will have them sign a written consent form at the time of baseline study interview. We will make it clear to the patient and family member that both individuals must be eligible and provide informed consent for either to be eligible to participate in the study. An RA/Study coordinator will obtain informed written consent for all eligible and interested dyads.

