(If unable to answer question 1 above, ask the following questions)		
1a) "Have you experienced swelling of the legs or ankles due to excess fluid?"	YES	NO
1b) "Do you sleep on more than one pillow at night to help you breathe easier?"	YES	NO

TO BE COMPLETED BY RESEARCH ASSISTANT ELIGIBILITY CRITERIA—for Heart Failure Patients

Patients must have ALL of the following eligibility criteria.

1. Relationship – Patient must be seen by a health care provider at the UNC Cardiology clinic at least one time before? YES
2. Diagnosis – Carry a clinical diagnosis of Heart Failure or Diastolic Dysfunction YES
3. Medications– Currently prescribed a loop or Thiazide diuretic. YES

Loop Diuretics: Bumetanide (Bumex®), Torsemide (Demadex®), Furosemide (Lasix®)

Thiazide Diuretics: Hydrochlorothiazide (HydroDIURIL®), Chlorothiazide (Diuril®), Chlorthalidone, Metolazone (Zaroxolyn®), Indapamide (Lozol®)

4. Symptoms – Have New Class II, III or IV symptoms now or in the past 6 months YES
5. Age – Over the age of 21 YES
6. Communication – Speak English and have adequate hearing to communicate and talk in person or on the phone. YES
7. Audiotaping – Must agree to have a visit audiotaped YES

INELIGIBILITY CRITERIA

Patients will be ineligible if they meet ONE of the following criteria:

1. Do not speak English
2. Have significant cognitive impairment (e.g. a diagnosis of dementia/severe cognitive impairment)
3. Have significant psychiatric impairment (e.g. schizophrenia)

4. Require assistance with Activities of Daily Living (ADL)
5. Live in a nursing home

IS THE PATIENT ELIGIBLE? (Circle one) ELIGIBLE INELIGIBLE

Partners In Health Eligibility SCREENING FORM

The following form will be used to determine eligibility for Family Members:

Research Assistant: _____

Study ID#: _____

QUESTIONS TO ASK INDIVIDUAL TO VERIFY ELIGIBILITY

1. "What is your current age?" _____
Family member must be at least 18 years old.

2. "What is the highest grade you completed?" _____
(If 6th grade or below, or if have knowledge that family member is illiterate, have witness present when signing consent)

3. Do you have a working telephone or live with the patient?
YES NO

4. "Is English your preferred language?"
YES NO

If family member does not speak English, then they are ineligible to participate.

The family member and the patient MUST answer YES to the following question for the visit companion to be eligible to participate.

Read the following definition to the participant:

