6.3 Statistical Methods

Analysis for this study will be quantitative pre-post analyses. We will compute descriptive statistics (percentages, means, and standard deviations) for feasibility, acceptability, and behavioral outcomes. For each behavioral outcome (HF self-care behaviors, self-efficacy related to self-care, communication with provider, communication with providers, and perceived efficacy in interactions with doctor), we will use paired t-tests to compare changes in mean scores from baseline to 1-month separately for accompanied patients, companions, and unaccompanied patients. In this pilot study, we are not conducting hypothesis testing. To help plan for future proposals, point estimates of effect sizes for the mean change value in each behavioral outcome will be computed as the ratio of the mean difference in each change value between baseline and 1-month follow-up.

6.4 Sample Size and Power.

This is a pilot study and as such, our sample size was selected based largely on feasibility. Specifically, we examined the expected margin of error for varying recruitment and recruitment yields.

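### Section 6.1 defines the primary outcome on eligible patients but sets its 50% aim on screened patients, and some refusals are classed as ineligibility

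*Combined protocol and SAP*

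**What the plan says.** **Outcome and aim.** Section 6.1 gives the primary endpoint as "Primary outcome= Percent of eligible patient participants who enrolled in the study". Two sentences later it gives the target: "The investigators aim to have at least 50% of screened patients consent and enrollment". The Efficacy Evaluations row of the synopsis has "Percent of eligible patients and companions who enrolled in the study", without saying whether the unit is the person or the dyad.

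**Eligibility.** The patient screening form in section 4.1 lists among its eligibility criteria "Must agree to have a visit audiotaped", an item absent from the patient list in 3.4. Section 3.4 makes willingness and consent eligibility criteria for the family member. The recruitment text in 4.1 tells dyads that "both individuals must be eligible and provide informed consent for either to be eligible to participate in the study".

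The two patient lists differ in three places:

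| Item | Section 3.4 | Screening form |
|---|---|---|
| Age | 30 or older | over 21 |
| Diuretic | "Currently prescribe a loop diuretic" | loop or thiazide |
| Clinic | Cardiology or General Internal Medicine | Cardiology |

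**Records.** Section 4.7 has the screening forms of refusers and ineligible people destroyed within one week. It keeps one list of names of those approached who were either ineligible or not interested, so that they are not approached again.

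**The concern.** Enrolment rate is the pilot's primary outcome and its only feasibility measure with a numeric target. Followed as written, 6.1 computes a rate on one base and judges it against a target stated on another. The same recruitment data could then be reported as meeting or missing 50%, and the choice could be made after the counts are known.

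Two features make this worse. Some people who decline are removed from the eligible denominator, when their declining is what a feasibility rate should show. And once forms are destroyed, the split between eligible refusers and ineligible people may have to be estimated at reporting.

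**Working it through.** **Inputs.** From the documents: the 50% aim (6.1) and the cap of 30 dyads (3.3). Not given: the number screened, the eligible share e, and the number and kind of refusals. Those are assumed below and labelled so. There is no figure to reproduce: the 50% is a declared aim, and the margins of error and yields mentioned in 6.1 and 6.4 are not reported.

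**Step 1: when the two bases disagree.** Let N be patients screened, E = eN eligible, and n enrolled. Then n/N = e × (n/E), so the screened-based rate can never exceed the eligible-based one. The aim is met on eligible patients and missed on screened patients when 0.5 ≤ n/E < 0.5/e.

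| e (assumed) | Upper end of disagreement, 0.5/e |
|---|---|
| 1.0 | 50% (no disagreement) |
| 0.9 | 0.5/0.9 = 55.6% |
| 0.8 | 0.5/0.8 = 62.5% |
| 0.7 | 0.5/0.7 = 71.4% |

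At e = 0.5 the screened-based aim requires every eligible patient to enrol. Below 0.5 it cannot be met.

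**Step 2: at the cap.** With 30 enrolled, 30/0.5 = 60. The aim is met if at most 60 are screened (one base) or at most 60 are eligible (the other). Sixty eligible corresponds to 60/e screened, which is 75 at e = 0.8.

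**Step 3: illustration.** Assume 75 screened, 52 meeting the patient criteria and 30 enrolled (e = 52/75 = 0.69).

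- Screened base: 30/75 = 40.0% (95% Wilson interval 29.7 to 51.3).
- Eligible base: 30/52 = 57.7% (44.2 to 70.1).

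The point estimates fall on opposite sides of the aim. Both intervals include 50%, so the conflict is between the reported figure and the aim.

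**Step 4: refusals counted as ineligibility.** Assume 60 otherwise eligible patients, of whom 20 enrol and 40 are lost to refusal. Let r be the share of those losses due to audiotaping or a companion's declining. The rate is 20/(60 − 40r).

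| r (assumed) | Reported rate |
|---|---|
| 0 | 20/60 = 33.3% |
| 0.25 | 20/50 = 40.0% |
| 0.5 | 20/40 = 50.0% |

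Recruitment of one patient in three would reach 50% if half of the refusals were of these kinds.

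**Step 5: patients with no eligible companion.** If 8 of the 52 in step 3 (assumed) have none and are removed as ineligible, the rate becomes 30/44 = 68.2% (53.4 to 80.0). The plan does not say how they count.

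**Step 6: what the retained list can support.** With 30 enrolled and 50 names on the mixed list (assumed), 30/80 = 37.5% is the rate among everyone approached. The eligible-based rate is at least that. How much higher depends on how many of the 50 were ineligible, and the list is not stated to show this.

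**The case against.** **The case for leaving it alone.** Screened may be shorthand for screened and found eligible. Providers confirm the diagnosis and flag usual accompaniment before anyone is approached, so e may be near 0.9, where the disagreement spans only 50% to 55.6%. This is a pilot without hypothesis testing, and no go/no-go rule rests on the result. The form is stated to determine eligibility, so the working eligible set can be identified. Nothing forbids a tally before a form is destroyed.

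Much of this stands as a limit on size. It does not remove the mismatch: no text equates the two terms, and a form with several exclusions plus a screen-failure section shows that ineligible people are expected. That 4.7 leaves no usable record is partly an inference from silence; the firm statement is that no such record is named.

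**Stronger readings a reader might infer, which the documents do not support.**

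- *That patients excluded by providers swell the screened count.* Section 4.1 says "For patients deemed ineligible by providers, we will ask providers to provide reasons why the patients should not be contacted", but only provider-approved patients then go to the research assistant for eligibility assessment, and 11.1 places screening at that assessment, with the eligibility form. The ordinary reading leaves provider exclusions out.
- *That the dyad consent rule makes the rate complete by construction.* That sentence is an explanation to dyads about joint participation. The same recruitment text treats being eligible and being interested as separate, 4.7 separates refusal from ineligibility, and general consent is not among the patient form's criteria. A patient's general refusal therefore stays in the denominator.
- *That 6.3 contradicts the dyad rule by analysing outcomes "separately for accompanied patients, companions, and unaccompanied patients".* Unaccompanied can describe attendance at the visit. The baseline questionnaire has a branch for patients whose companion will not come, and a family member can enrol without being present at the clinic.

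**Conclusion.** The concern holds in this form. The numeric aim in 6.1 does not apply to the outcome that 6.1 defines, and the synopsis gives a third version with no unit. The size depends on e, which the documents do not give: the band of contradictory answers is 5.6 percentage points wide at e = 0.9, 12.5 at 0.8 and 21.4 at 0.7. Declining audiotaping and a companion's declining are treated as ineligibility, which can only raise the eligible-based rate; by how much is unknown. The differences between 3.4 and the form on age, diuretic and clinic matter here because they change who is counted as eligible.

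Confidence is high for the mismatch of bases. It is lower for the practical loss from 4.7, since staff may keep a tally that the plan does not describe. All screened, eligible, refusal and list counts in the illustrations are assumptions. This should be fixed. It does not invalidate the pilot.

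**What to change.** 1. In 6.1 and the synopsis, state one unit and one denominator (for example, patients assessed by the research assistant who meet the patient criteria), and apply the 50% aim to that same ratio.
2. Report enrolled-to-screened as a secondary figure, with screened defined as assessed with the eligibility form, in line with 4.1 and 11.1.
3. For this outcome, count declining audiotaping and a companion's declining as refusal. Both can remain conditions of entry; only the counting changes. State how patients with no eligible companion are counted.
4. In 4.7, before each form is destroyed, enter one de-identified log line: eligible, ineligible or not assessed; the criterion failed; and who declined.
5. Reconcile 3.4 with the screening form. This review does not say which version is right.

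The cost is wording changes in these sections and a small logging task, with no change to sample size or visits. The reported rate may be less favourable. The log line is the urgent part, because the information may not be recoverable after a form is destroyed.

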6.2 Secondary Endpoint

Secondary outcomes include: 1) mean score on acceptability checklist; 2) mean score on self-care of heart failure index scores (maintenance, management, and confidence subscales); 3) mean score on caregiver contribution to self-care of heart failure index scores (maintenance, management, and confidence subscales); 4) mean score on perceived efficacy in patient-physician interactions score; 5) mean score on communication with physicians measure

6.3 Statistical Methods

Analysis for this study will be quantitative pre-post analyses. We will compute descriptive statistics (percentages, means, and standard deviations) for feasibility, acceptability, and behavioral outcomes. For each behavioral outcome (HF self-care behaviors, self-efficacy related to self-care, communication with provider, communication with providers, and perceived efficacy in interactions with doctor), we will use paired t-tests to compare changes in mean scores from baseline to 1-month separately for accompanied patients, companions, and unaccompanied patients. In this pilot study, we are not conducting hypothesis testing. To help plan for future proposals, point estimates of effect sizes for the mean change value in each behavioral outcome will be computed as the ratio of the mean difference in each change value between baseline and 1-month follow-up.

6.4 Sample Size and Power.

This is a pilot study and as such, our sample size was selected based largely on feasibility. Specifically, we examined the expected margin of error for varying recruitment and recruitment yields.

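### Section 6.3 prescribes paired t-tests while disclaiming hypothesis testing, and plans no confidence interval for any change score

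*Combined protocol and SAP*

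**What the plan says.** For the behavioral outcomes, section 6.3 says "we will use paired t-tests to compare changes in mean scores from baseline to 1-month", "separately for accompanied patients, companions, and unaccompanied patients". The outcomes are listed as "HF self-care behaviors, self-efficacy related to self-care, communication with provider, communication with providers, and perceived efficacy in interactions with doctor", so communication appears twice and four are distinct. The following sentence reads "In this pilot study, we are not conducting hypothesis testing". The section also plans means and standard deviations, and point estimates of effect size to inform later proposals.

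Section 6.2 gives the scores behind these outcomes. There are three subscales of the patient self-care index, three of the caregiver version, a perceived-efficacy score and a communication score.

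Nowhere in section 6 is there a significance level, a choice of one- or two-sided testing, a multiplicity rule, a confidence interval for a change score, or a statement on how a p-value would be reported. The margin of error mentioned in 6.1 and 6.4 concerns recruitment, not change scores. The primary outcome in 6.1 is the percentage of eligible patients who enrol.

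**The concern.** An analyst who runs the t-tests acts against the disclaimer. An analyst who follows the disclaimer has no stated way to express uncertainty in a mean change. The planned standard deviations describe the spread of scores, and the effect sizes are point estimates, so neither shows how precisely a mean change is known.

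This matters because section 2 includes the effects of the prompt list among the study's objectives, and section 12 plans a paper on the primary and secondary outcomes. If t-test results were the only inferential output, a chance low p-value among many could be taken as a signal, and a high one could hide a change of useful size. The design is single-group pre-post (section 3.1), so even a small p-value could not be attributed to the prompt list. For planning a later trial, the mean change and its precision are what is needed.

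**Working it through.** The plan states no test count, significance level or error rate, so there is no figure of its own to reproduce.

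**Counting tests** (sections 6.2 and 6.3, and the baseline and follow-up measure lists in section 4)

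- Accompanied patients: 3 self-care subscales (the confidence subscale is the self-efficacy outcome), 1 communication score and 1 perceived-efficacy score = 5.
- Companions: 3 caregiver subscales and 1 perceived-efficacy score = 4. The companion baseline list has no communication measure. These four are inferred, because the 1-month list in section 4.2 is headed as a patient questionnaire and no companion list is given.
- Unaccompanied patients: 5, as for accompanied patients. This group may be empty, because the recruitment text in section 4.1 requires both dyad members to be eligible and to consent.

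Total without an unaccompanied group: 5 + 4 = 9. Total with one: 5 + 4 + 5 = 14. Counting the four distinct outcomes in three groups gives 12, which lies between.

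**False positives if nothing changes.** The level of 0.05, two-sided per test, is an assumption.

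- Expected number = k × 0.05, whatever the correlation: 9 × 0.05 = 0.45; 14 × 0.05 = 0.70.
- Chance of at least one, independent tests = 1 − 0.95^k: 1 − 0.95^9 = 0.370; 1 − 0.95^14 = 0.512.
- Chance of at least one, correlated tests, from 20,000 simulated data sets per setting. Correlations between change scores were assumed to be 0.3 to 0.7 within a person and 0.1 to 0.4 within a dyad. The result is about 0.25 to 0.35 for 9 tests and 0.36 to 0.48 for 14. Group sizes between 10 and 30 made little difference.

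Scores from the same person and dyad are likely to be positively correlated, so the independence figures are best read as ceilings.

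**Precision of a mean change.** The half-width of the 95% interval, in units of the SD of change, is t(0.975, n−1)/√n:

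| Complete pairs | Half-width (SD of change) |
|---|---|
| 30 | 0.37 |
| 20 | 0.47 |
| 15 | 0.55 |

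Thirty is the best case, since the plan enrols up to 30 dyads. Loss to follow-up would reduce the number of pairs. The symptom-recognition item in the management section can also be answered as not applicable by patients without recent symptoms.

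**The case against.** The strongest reply is that this is loose wording, not an analysis error. A paired t procedure also yields the mean change, its standard error and an interval, and the disclaimer can be read as ruling out confirmatory claims only. That reading is reasonable, and the replacement text adopts it. But section 6.3 does not say so. It names the test, omits the interval, and leaves an analyst to guess.

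A reader might infer that effects will be judged by which p-values fall below 0.05, or that non-significant results will be taken as no effect. The documents do not support this: section 6 contains no threshold and no rule for success on these outcomes, and section 6.2 defines them as mean scores. It is a foreseeable misuse, not a stated plan.

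A reader might also fault the plan for lacking power or a named key behavioral outcome. That does not apply to a pilot whose primary outcome is enrolment and whose sample size, by section 6.4, rests largely on feasibility.

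Two further objections stand. Fourteen is a derived upper count, and five of those tests belong to a group that may not exist. And intervals do not remove multiplicity: the same number of unadjusted 95% intervals has the same chance that at least one excludes zero. The case for intervals is that they show precision; they still have to be labelled unadjusted.

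**Conclusion.** The contradiction is real and sits in adjacent sentences of section 6.3. The absence of any interval for change scores makes it more than a matter of style. Its size is moderate: about 9 to 14 tests, with 0.45 to 0.70 expected false positives. The chance of at least one is 37% to 51% under independence, and about 25-35% (9 tests) or 36-48% (14 tests) under the correlations simulated.

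These figures rest on an assumed two-sided 0.05, no true change, inferred companion 1-month measures and, for 14, the existence of unaccompanied patients. They show what unlabelled tests would risk. They do not show that the plan intends to make such claims, and they do not call for a multiplicity correction in a study that disclaims testing. The primary enrolment outcome is not affected.

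**What to change.** In section 6.3, replace the paired t-test sentence with the text below. It keeps the outcome list and the analysis by group.

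> For each behavioral outcome [present list retained, with communication named once], we will report the mean paired change from baseline to 1 month with its t-based 95% confidence interval. Accompanied patients, companions and, if any are enrolled, unaccompanied patients will each be summarized on their own. Intervals are descriptive and unadjusted for multiplicity. No outcome will be declared changed on the basis of statistical significance, and any p-value shown will be labelled descriptive.

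Keep the sentence that disclaims hypothesis testing. A complete ban on p-values is not needed, since labelling them descriptive also resolves the contradiction.

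The cost is a short wording change, with no new data, sample size or multiplicity procedure. The sponsor gives up the option of claiming 'significant' pilot effects, which the plan already disclaims.
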